### 8.2 Subject disposition

All subjects who entered the extension study will be included in a summary of subject accountability. The number of subjects entering the extension study, the frequency and percentage of subjects randomised, in the Safety population, in the ITT population and in the PK population will be summarised by treatment regimen and overall.

Subject disposition information will be summarised by treatment regimen and overall. The number of subjects completing and withdrawing from the treatment period (up to and including Visit 7) and the number of subjects completing and withdrawing from the study will be tabulated. Reasons for treatment discontinuation and discontinuation from the study will also be presented.

The follow-up time will be summarised descriptively.

### 8.3 Protocol deviations

The number of subjects excluded from ITT, Safety and PK populations and reasons for exclusion will be summarised by treatment regimen and overall.

All protocol deviations identified during MBGS206 will be summarised descriptively by treatment regimen and overall.

Summaries will be conducted on all subjects that were randomised

### 8.4 Demographics and baseline characteristics

No formal comparison between treatment regimens on demographics and baseline characteristics will be conducted.

#### 8.4.1 Demographics

Demographic variables captured at the start of study MBGS205 will be listed and summarised for subjects entering the extension study by treatment regimen and overall. This will include age, sex, race, weight, height and BMI. Separate summaries will be produced using the Safety and ITT populations.

#### 8.4.2 Baseline and disease characteristics

Duration of HH disease (years) and the number of subjects receiving previous treatment and each item on the Androgen Deficiency Symptom Checklist captured at the start of study MBGS205 will be summarised descriptively by treatment regimen and overall.

Total testosterone at initial diagnosis, first and second screening visits and the average testosterone over the first and second screening visits from study MBGS205 will be tabulated.

In addition baseline total testosterone (absolute values and number of subjects above and below 200 ng/dl), free testosterone (absolute values and number of subjects above and below 47 pg/mL), bioavailable testosterone (absolute values and number of subjects above and below 130 ng/dl), oestradiol, DHT, inhibin A, inhibin B, HBA1c, sex hormone binding globulin (SHBG), fasting lipid profile (total cholesterol, low density lipoprotein [LDL], triglycerides and HDL), Vitamin D,

IIEF domain scores, IIEF erectile function domain severity and PROMIS sexFS domains will be summarised descriptively by treatment regimen and overall.

All Summaries will be produced using the Safety Population and ITT Population.

### **8.4.3 Medical history**

A summary of all medical history captured from Study MBGS205 will be presented by Medical History Code (as per CRF), system organ class (SOC) and preferred term (PT), by treatment regimen and overall using Medical Dictionary for Regulatory Affairs® (MedDRA) Version 19.1 or higher.

In addition the number of subjects with an MRI of pituitary performed, the MRI finding (Normal, Abnormal NCS or Abnormal CS) and the number of subjects who have had a vasectomy will be summarised.

All Summaries will be produced using the Safety Population.

### **8.4.4 Prior, Concomitant and Follow-up medications**

All medications (taken across both MBGS205 and MBGS206) will be coded using the World Health Organization (WHO) Drug Dictionary (March 2016 or later) and will be summarised by Anatomical Therapeutic Chemical (ATC) classification level 4 and Preferred Name by treatment regimen and overall for the Safety population.

Summaries of Prior medications to active study medication, concomitant to active study medication (i.e across both MBGS205 and MBGS206), concomitant to MBGS206 study medication and follow-up medications will be presented.

### **8.4.5 Concomitant Procedures**

Concomitant procedures to active study medication (i.e across both MBGS205 and MBGS206) and concomitant procedures to MBGS206 study medication will be summarised by Procedure Name, treatment regimen and overall for the Safety population.

## **8.5 Extent of exposure**

### **8.5.1 Treatment duration**

Duration of treatment (in days) for active study medication and just MBGS206 study medication will be categorised in intervals and summarised descriptively by treatment regimen on the Safety population using descriptive statistics.

### **8.5.2 Treatment compliance**

The overall treatment compliance (in %) of active study medication and just MBGS206 study medication will be presented by treatment regimen using the Safety population. The number of subjects with overall compliance <80% or >120% will be presented.

### 8.6 Efficacy analyses

This section addresses the analyses to be conducted on the secondary and exploratory efficacy endpoints.

All definitions relative to efficacy and exploratory endpoints are detailed in Section 7.1.3.

Analyses will be conducted separately for subjects that were randomised to active treatment and subjects that were randomised to placebo treatment in study MBGS205.

#### 8.6.1 Analysis methods

For binary outcomes the proportion of subjects with a response will be summarised and compared between treatment regimens using Fisher's Exact Test.

For continuous parameters, the change from baseline will be summarised by treatment arm and visit. A single sample 2-sided t-test conducted at the 5% significance level will be used to analyse the change from baseline to Week 48 within each treatment arm. In addition, the change from baseline will be assessed with a mixed model repeated measure (MMRM) analysis. Analyses will include the fixed, categorical effects of treatment, visit, and treatment-by-visit interaction, as well as the continuous, fixed covariates of the associated baseline value and baseline-by-visit interaction. An unstructured covariance matrix will be used to model the within-subject errors. If the model with the unstructured covariance matrix fails to converge, other covariance structures, including Toeplitz, compound symmetry, and spatial power, will be considered. The denominator degrees of freedom will be calculated according to the Kenward-Roger method. Significance tests for treatment differences will be based on least-squares means.

Associations between changes in PROs and changes in body composition, physical activity, sleep, and grip strength will be assessed with correlation coefficients and with separate linear regression models in which changes in PRO measure total or subscale scores will be taken as the predictor variable, and baseline score as a covariate. The associations between changes in testosterone and changes in PROs, body composition, physical activity, grip strength, and sleep will be assessed in the same way. Correlation coefficients, Beta coefficients, standard errors, and 95% CIs will be presented.

##### 8.6.1.1 Multiplicity

Treatment regimens will be assessed by pairwise comparisons. No adjustment will be made for multiple comparisons and all analyses are considered exploratory.

##### 8.6.1.2 Treatment by centre interaction analysis (multi-centre study)

No analysis will be made to assess the treatment-by-centre interaction.

#### 8.6.2 Analysis of primary endpoint

The Primary Endpoint is defined as the change in lumbar bone density measured by DEXA from baseline in Study MBGS205 to Week 48 in Study MBGS206 by dose group in subjects randomised to active treatment in Study MBGS205.

DXA Scan assessments will only be performed at the EOT visit (for subjects that reached at least Week 36) and will be over-read by IMI. The DEXA over-read data will be used for the primary endpoint statistical analysis.

Descriptive statistics (observed values, changes from baseline and percentage change from baseline) in lumbar bone mineral density will be presented for each treatment regimen and time-point. A single sample 1-sided t-test conducted at the 2.5% significance level will be used to analyse percentage change from Baseline (MBGS205) to Week 48 (MBGS206) LOCF in each treatment arm to test the null hypothesis that the percentage decrease from Baseline is  $\leq 3\%$ . P-values and associated CI will be presented.

Only subjects included in the safety population that have a post-Baseline DEXA assessment in MBGS206 and were randomised to active treatment in Study MBGS205 will be included in this analysis. The analysis will be repeated for subjects included in the completer population.

Observed and percentage change from baseline values at each visit will be presented in a line graph by treatment group.

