Use of aromatase inhibitors in women with breast cancer have been associated with reduction in bone mineral density and risk of fracture. This is attributed to the oestrogen lowering effects in post-menopausal women. The potential for BGS649 to affect bone in obese males with hypogonadism is expected to be less as oestrogen levels are similar to those in pre-menopausal women and only 25% oestradiol reduction was observed after 12 weeks of BGS649 0.3 mg loading dose and 0.1 mg weekly. There may be other factors that reduce sensitivity to aromatase inhibition on bone in this population as bone mineral density increases with increasing BMI, and bone anabolic effects are expected with the normalisation of testosterone.

Understanding any potential effect is a critical element to the risk/benefit profile of BGS649. Bone turnover biomarkers and bone mineral density are being assessed in MBGS205, however 6 months is too short duration to assess bone mineral density. Study MBGS206 will be a 6 month extension of Study MBGS205 to measure the effects of 12 months treatment with BGS649 on bone mineral density.

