13.5 Description of Statistical Analyses

13.5.1 General Considerations

All analysis will be considered as exploratory analysis.

At the time of unblinding of the MBGS205 study, ICON will also be unblinded to MBGS206 treatment assignment. At this time analysis maybe conducted to support MBGS205 reporting. As all analysis will be considered exploratory there will be no adjustment for multiplicity.

The statistical evaluation will be performed by ICON using SAS®, Version 9.3 or later. Data will be analysed by either enumeration of subjects displaying distinctive characteristics within each treatment regimen or by descriptive statistical summaries such as means, SD, medians, and ranges for continuous measures. Categorical variables will be presented by the number of observations and absolute and relative (%) frequency.

For efficacy data summary statistics (N, mean, SD, median minimum and maximum for continuous data, and N [%] for categorical data) will be presented at each visit.

Similarly, changes from Baseline (or percentage change from Baseline if appropriate) will be summarised in a similar manner.

The main population for efficacy analysis will be the ITT population.

Unless stated otherwise, for subjects randomised to active treatment in Study MBGS205, change in the extension study MBGS206 will be measured against their Baseline assessments in Study MBGS205 for subjects randomised to placebo in Study MBGS205, unless stated otherwise, Baseline will be the last value prior to first dose of study medication in Study MBGS206.

Data in summary tables will generally be presented on an Observed Cases basis.

The analysis of the primary safety endpoint will be 1-sided test conducted at the 2.5% significance level. Unless stated otherwise, all other statistical tests will be 2-sided and conducted at the 5% level, and all quoted CIs will be 2-sided 95% CIs. All 3 treatment arms will be assessed by pairwise comparisons made.

Full details of the statistical analysis will be given in a statistical analysis plan (SAP).

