13.5.2 Analysis of Primary Endpoint

The percentage change from Baseline in lumbar bone mineral density measured in g/cm² by DEXA will be summarised by dose group and visit. A single sample 1-sided t-test conducted at the 2.5% significance level will be used to analyse percentage change from Baseline (MBGS205) at Week 48 (MBGS206) in each treatment arm to test the null hypothesis that the percentage decrease from Baseline is $\leq 3\%$. Only subjects that have a post-Baseline DEXA assessment in MBGS206 will be included in this analysis.

The primary analysis will be performed using the safety population.

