13.5.5 Safety Analyses

The analysis of safety parameters will be based on the safety population. In general, missing safety data will not be replaced. A more detailed description will be presented in the SAP.

Adverse Events

AEs will be coded using the most recent version available of the Medical Dictionary for Regulatory Activities (MedDRA). Summaries will be by system organ class and preferred term. TEAEs are defined as any AE occurring or worsening on or after the first dose of study medication. Further details of this will be provided in a SAP. If a subject experiences the same preferred term multiple times, then the event will be counted only once and by the greatest severity.

The frequency and incidence of TEAEs will be presented by system organ class and preferred term for each treatment regimen (number and percentage of subjects experiencing at least 1 AE per preferred term as well as the number of observed events per preferred term). Separate tables will be presented by severity and by relationship. All AEs will be presented in full in a comprehensive listing including subject number, treatment regimen, severity, seriousness, action taken, outcome, relationship to treatment, onset/stop, and duration. Details of SAEs and AEs leading to withdrawal will be listed separately.

Concomitant Medication

Concomitant medication will be tabulated and summarised by treatment regimen.

Physical Examination

Physical examination results will be listed by subject and body system.

Vital Signs

Vital signs will be summarised as actual values and change from Baseline by treatment regimen and visit.

ECG

The overall ECG interpretation will be summarised by presenting the number and percentage of subjects with “Normal”, “Abnormal, not clinically significant”, and “Abnormal, clinically significant”.

ECG parameter values (e.g., QT_cF) will be summarised as actual values and change from Baseline by treatment regimen and visit to end of treatment.

Clinical Laboratory

Descriptive statistics will be presented for quantitative laboratory parameters for each treatment regimen and time-point. Similarly, changes from Baseline will be summarised.

Values outside the normal range will be categorised as H (above the normal range) or L (below the normal range) based on the laboratory’s reference range and these will be flagged in the listings of individual subject data.

Withdrawals

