## 7.2 Handling of missing data and outliers

### 7.2.1 Missing data analysis methods

Unless specified, data in summary tables will be presented using Observed Case (OC) data and therefore no missing data will be imputed.

For specified endpoints a last observation carried forward (LOCF) imputation will be utilised. In this approach subjects with a missing observed value at a visit will be imputed with the last non-missing, post-baseline value.

For each continuous exploratory endpoint, the change from Baseline will be assessed with a mixed model repeated measure (MMRM) analysis.

For data listings, unless specified, all data will be presented as they have been recorded (e.g. missing and partial dates will not be replaced).

---

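### SAP 8.6.2 puts undeclared LOCF into the primary lumbar BMD test, and the Appendix F windows leave early end-of-treatment scans unassigned, so a Week 24 scan could stand for Week 48

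*SAP*

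**What the plan says.** **Protocol.** Section 13.5.2 tests "percentage change from Baseline (MBGS205) at Week 48 (MBGS206) in each treatment arm" with a one-sample, 1-sided t-test at 2.5% against a decrease of 3% or less. It mentions no imputation. Its entry rule is: "Only subjects that have a post-Baseline DEXA assessment in MBGS206 will be included in this analysis". Two general statements surround it: "Data in summary tables will generally be presented on an Observed Cases basis" (13.5.1) and "In general, missing safety data will not be replaced" (13.5.5). Section 12.4 provides a DEXA scan after an early stop only if the man reached Week 36.

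**SAP.** Section 8.6.2 keeps the test and the entry rule but analyses "percentage change from Baseline (MBGS205) to Week 48 (MBGS206) LOCF in each treatment arm". Section 7.2.1 defines LOCF: "subjects with a missing observed value at a visit will be imputed with the last non-missing, post-baseline value". For men randomised to active drug in MBGS205, section 8.1.5 sets baseline in MBGS205, so their Week 24 scan is a post-baseline value. Section 8.7.1 says the DXA analyses use the Appendix F windows. For active men these are Day 140 to Day 196 for Week 24 (target Day 168) and Day 308 to end of study for Week 48 (target Day 336). Section 9 lists three changes from the protocol: an added lumbar endpoint for former placebo subjects, the vitamin D cut-off, and the site 1156 sensitivity analyses. LOCF is not among them.

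**The concern.** The study exists to measure bone density after 12 months of drug. Protocol 7.1 gives the reason for the extension: "6 months is too short duration to assess bone mineral density". If a 6-month scan enters the primary test as a 12-month value, the test answers a different question for that man.

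The SAP does not say which scan LOCF carries when a man has a scan between Day 252 and Day 307. One programmer might carry that scan. Another, working from windowed visits, would find no value at Week 48 and go back to Week 24. Both would be following the text. The choice affects the headline p-value in each dose arm, and it should not be left until the data are in hand.

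**Working it through.** **1. The gap in the windows.** Week 36 is 36 x 7 = Day 252. Week 44 is 44 x 7 = Day 308, the first day of the Week 48 window. The Week 24 window ends on Day 196. An early end-of-treatment scan on Day 252-307, which is 75% to about 92% of the 48-week exposure, therefore falls in no window.

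**2. Who is affected.**
- Stopped before Week 36: no MBGS206 scan after its Baseline, so not in the test.
- Scanned on Day 252-307: in the test, with no windowed Week 48 value. LOCF carries either this scan or the Week 24 scan; the SAP does not say which.
- Scanned on Day 308 or later: windowed as Week 48, no carry needed.

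**3. The plan's own figures.** The protocol synopsis has 30 men entering per arm with about 17% dropout: 30 x 0.83 = 24.9, so about 25 completers and 5 dropouts. Protocol 13.1 gives SD 0.0439 g/cm2, 2-sided 5%, 90% power and N = 25; section 7.2.1 gives a 3% decrease. Baseline BMD is not given. Assuming 1.0 g/cm2, 3% is 0.030 g/cm2, and the one-sample t-test (noncentral t) of that change against zero needs N = 25, with power 0.906. Other assumed baselines give N = 30 (0.90), 27 (0.95), 23 (1.05) and 18 (1.20). On the 1.0 assumption the SD is 4.39%.

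**4. Effect if the Week 24 scan is carried.** Assumptions, none of them in the documents: loss is linear, the true 48-week loss is L = 6%, and k = 1 to 3 men per arm are scanned on Day 252-307 in addition to 25 men observed at Week 48. With N = 25 + k and p = k/N:
- mean = L x [1 - p x (1 - 24/48)]
- SD of the mixture = sqrt(4.39^2 + p(1 - p) x 3^2), because carried men average 3 points less loss
- power = noncentral t, 1-sided 2.5%, difference = mean - 3

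| k | N | Mean loss | SD | Power |
|---|---|---|---|---|
| 0 (observed only) | 25 | 6.00% | 4.39 | 0.906 |
| 1 | 26 | 5.88% | 4.43 | 0.891 |
| 2 | 27 | 5.78% | 4.46 | 0.876 |
| 3 | 28 | 5.68% | 4.49 | 0.861 |

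On this route, adding men to the analysis lowers power.

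**5. Effect if the early scan itself is carried.** Take 3 of 28 men scanned at Week 40: mean = 6 x [1 - (3/28) x (1 - 40/48)] = 5.89%, SD 4.40, power 0.918. The extra subjects slightly more than offset a shift of 0.1 point.

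**The case against.** The case on the other side is substantial.

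- **The protocol does not forbid LOCF.** Section 13.5.2 is silent, 13.5.1 concerns summary tables, and both general statements are qualified. Section 13.5.5 also defers detail to the SAP. The protocol orders early end-of-treatment scans and admits any man with an MBGS206 scan after Baseline, so those scans were evidently meant to count. This stands. What remains is that a change to the primary test belongs in section 9.
- **A Week 24 scan alone does not admit a man.** A reader might infer that all 5 expected dropouts of 30 could be carried from Week 24, giving 6 x [1 - (5/30) x 0.5] = 5.5% and power of about 0.83. The documents do not support that. The Week 24 scan is the MBGS206 Baseline, and it also decides eligibility on bone density, so counting it as post-Baseline would leave the entry rule excluding almost nobody. The window gap is a narrower route, open only to men who have a later scan.
- **The direction of error is not established.** A reader might infer that bone loss will be understated. That needs continuing loss after the carried scan. With stable BMD the shift is zero; with a gain it reverses. If men who stop early lose bone faster, an analysis of observed Week 48 scans alone could be the more biased one.
- **Analyses without LOCF exist.** SAP 8.6.2 repeats the test in completers, who must have a Week 48 assessment, and 8.7.1 plans an MMRM of lumbar BMD. All analyses are declared exploratory. These soften the problem without settling it. The completer repeat leaves out early stoppers, and the MMRM uses the same windows and states no test against 3%.

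**Conclusion.** The point holds in limited form. SAP 8.6.2 adds LOCF to the primary test without declaring it, and Appendix F leaves scans on Day 252-307 unassigned, so the SAP permits a 6-month scan to be analysed as a 12-month value when a later scan exists.

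If that happens and loss is progressive, the understatement is modest: about 0.1 to 0.3 percentage points at a true 6% loss, with power falling from 0.906 to between 0.89 and 0.86. These figures rest on linear loss, an assumed baseline of 1.0 g/cm2 and an assumed 1 to 3 affected men per arm. If the early scan is carried instead, there is no material effect. LOCF as such is therefore not shown to distort the primary result; the exposure comes from the unassigned scans.

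**What to change.** 1. In SAP 8.6.2 and Appendix F, state that the Week 24 scan is never carried to Week 48, and that a scan on Day 252-307 is used as that man's end-of-treatment value, with its actual day recorded.
2. Add a model of percentage change on actual scan day, using the baseline, Week 24 and end-of-treatment scans of all men randomised to active drug in MBGS205, and test the Day 336 estimate against 3%.
3. Show the observed Week 48 result beside the LOCF result in each arm.
4. Declare LOCF in section 9, with its reason.

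The cost is SAP wording and one extra model on scans already held. Removing early end-of-treatment scans from the main t-test altogether is not needed. That would be a trade-off, since the protocol's entry rule admits those men and they may differ from completers.

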9 INVESTIGATIONAL PLAN

9.1 Overall Study Design and Plan

9.1.1 Description

This is a 6 month, active treatment, extension study, open to subjects who have completed the full 24 week treatment period in Study MBGS205 (a Phase IIb multicentre, double-blind, dose-ranging, randomised, placebo-controlled study evaluating safety and efficacy of BGS649 in male obese subjects with HH).

The main purpose of this study is to evaluate bone mineral density in subjects after 12 months exposure with BGS649. The study will also collect additional BGS649 safety and efficacy data on subjects that were randomised to placebo in Study MBGS205 and have 6 months active drug exposure in Study MBGS206. The study design and schedule of assessments are summarised in [Figure 9-1](#) and [Table 9-1](#), respectively.

Subjects that completed full 24 weeks treatment period of Study MBGS205 will be invited to participate. Informed consent will be taken prior to study procedures being performed. Study participation will comprise of the Extension Study Baseline visit (Week 24 of Study MBGS205), 7 visits during the treatment period up to Week 48 (End of Treatment [EOT]), and a Follow-Up (FU) visit for safety performed at Week 60, 12 weeks after the Week 48/EOT visit. The End of Study is defined as the last visit of the last global subject.

Extension Study Baseline assessment:

The Extension Study Baseline assessment will be performed on a same day as the EOT visit of Study MBGS205. As applicable, EOT assessments of Study MBGS205 will be used for Baseline assessments of Study MBGS206 and do not need to be repeated. The results of liver biochemistry, PSA, haematocrit, and electrocardiogram (ECG) assessments performed at the Baseline visit (EOT of MBGS205) may not be available for eligibility assessment, therefore results of these parameters from last valid visit of Study MBGS205 will be used to enable recruitment and dosing. This includes any of the parameters from last scheduled or unscheduled visit, measured not longer than 1 month before Baseline visit/EOT of MBGS205. Bone density from EOT assessment of MBGS205 will be used for eligibility evaluation for MBGS206.

If results of liver biochemistry, renal function, PSA, haematocrit and ECG measured at Extension Study Baseline visit/EOT of MBGS205 are subsequently found to meet any study discontinuation criteria, the subject will be withdrawn.

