9.3 Selection of Study Population

9.3.1 Inclusion Criteria

1. Participating in Study MBGS205 and completion of the 24 week treatment period without meeting any discontinuation criteria of Study MBGS205
2. Agreement on the part of the subjects to use double-barrier contraception for vaginal sexual intercourse with female partners of child bearing potential to prevent conception and foetal BGS649 exposure from seminal fluid. To use single barrier protection (condom) to prevent semen exposure through non-vaginal sexual intercourse with female partners of child bearing potential and refrain from sperm donation for the duration of the study. All to be continued for at least 3 months following study drug discontinuation
3. Ability to understand and comply with the requirements of the protocol/study, including understanding and being able to give informed consent
4. In opinion of the investigator has been compliant with the requirements of the Study MBGS205 protocol.

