9.3.4 Study Drug Interruption and Discontinuation

Subjects may voluntarily discontinue investigational treatment for any reason at any time.

At the time of study drug discontinuation, the subject should have (as soon as possible) an EOT visit with the assessments that are normally done at the Week 48 visit (EOT, Visit 7). This should take place within 7 days after discontinuation of study drug. The reason for the discontinuation must be documented in the subject's medical records and entered on the appropriate electronic case report form (eCRF) page. All subjects who discontinue the study drug should enter the FU phase and attend the final follow up visit 12 weeks after EOT (FU, Visit 8).

Subjects will in addition be asked to provide a plasma and semen sample for PK at EOT (Visit 7), unless they are not able to provide this sample. This applies also to a subject discontinued because of elevated testosterone as determined by an unblinded physician. The investigator and study staff must discuss with the subject, the subject's continued participation in the study and request subjects to continue attending FU visits according to the study visit schedule.

If the subject cannot, or is unwilling to attend the FU visits, the site staff should request maintenance of regular phone contact with the subject, or with a person pre-designated by the subject. This phone contact should preferably be performed according to the study visit schedule. Data concerning the subject's health status, including information regarding new/concomitant treatments, AEs, AESIs (i.e., rash), and vital status will continue to be collected.

The investigator must also contact the IRT to register the subject's discontinuation from investigational treatment.

If the subject temporarily discontinues study drug because of AE or SAE or other relevant issue, the investigator should attempt to restart it as soon as possible after circumstances allow and in agreement with the Medical Monitor.

Investigational treatment MAY be permanently discontinued under the following circumstances:

1. Significant worsening of lower extremity oedema
2. Significant worsening of obstructive urinary symptoms

Investigational treatment MUST be permanently discontinued under the following circumstances:

3. If subject develops fragility fracture.

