12.4 DEXA Scan

Bone density will be evaluated with standard procedure described in study imaging manual. All evaluations during the study for particular subject should, where possible, be performed on the same machine with particular attention to ensuring consistency in positioning patients.

To assess the spine, the subject will be in supine position with legs supported on a padded box to flatten the pelvis and lower (lumbar) spine. To assess the hip, the foot is placed in a brace that rotates the hip inward. The detector will be slowly passed over the area separately for spine and hip, generating images. The duration of examination will be up to 30 minutes. DEXA T Score will be calculated based on actual measured bone density value. Both values will be evaluated for safety.

EOT DEXA scan: If the subject is discontinued from the treatment early, DEXA will be performed only if they reached minimum Week 36 (Visit 4) active treatment period. In order to accommodate scheduling, EOT DEXA can be performed within 5 days before the EOT visit

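### The primary lumbar BMD test leaves out every active-arm man who stops before Week 36, although each should have an on-drug Week 24 scan; if stopping is related to bone loss, 12-month loss is understated.

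*SAP*

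**What the plan says.** **Who enters the primary test.** Protocol 13.5.2: "Only subjects that have a post-Baseline DEXA assessment in MBGS206 will be included in this analysis". SAP 8.6.2 repeats the restriction for active-randomised men: "Only subjects included in the safety population that have a post-Baseline DEXA assessment in MBGS206".

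**Who gets a scan.** Protocol 12.4: "If the subject is discontinued from the treatment early, DEXA will be performed only if they reached minimum Week 36 (Visit 4) active treatment period". The schedules show no other DEXA in MBGS206 apart from the assessment transferred from MBGS205 as baseline.

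**A bone-related mandatory stop.** Protocol 9.3.4 lists, among reasons for permanent discontinuation, "If subject develops fragility fracture".

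**The Week 24 scan.** Protocol 9.1.1: "Bone density from EOT assessment of MBGS205 will be used for eligibility evaluation for MBGS206". Protocol 9.3.1 requires "completion of the 24 week treatment period without meeting any discontinuation criteria of Study MBGS205". SAP Appendix F gives active-arm men a Week 24 DEXA window (Days 140 to 196).

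**Other relevant provisions.** SAP 8.6.2 applies LOCF to the primary test. SAP 8.7.1 plans a repeated-measures model of BMD change in active-randomised men, with least-squares means by visit (through 8.6.3.3). SAP 8.1.1 assigns the BMD endpoints to the ITT and completer sets, whereas 8.6.2 and 8.7 use the Safety population.

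**The concern.** The objective is the effect of 12 months of BGS649 on bone density, and this t-test is the only test of the primary hypothesis. It describes men who stayed on drug at least to Week 36, not all the active-arm men who entered. The alternative hypothesis is a loss above 3%, so an understated loss does not err on the safe side: it makes harm harder to declare. A man who fractures at Week 30 contributes nothing to the test, although a scan taken after 24 weeks on drug should be on file for him.

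**Working it through.** **1. The rule, step by step.** A man who stops before Week 36 has no MBGS206 scan (Protocol 12.4), so he fails the entry condition of the t-test (SAP 8.6.2).
- LOCF does not bring him back, because the entry condition removes him before any value is carried forward. His Week 24 scan is an MBGS205 assessment that serves as the MBGS206 baseline, not a post-baseline scan in MBGS206.
- ITT does not bring him back: SAP 6.1 also requires a post-baseline lumbar value in MBGS206.
- The completer set (SAP 6.3) is narrower still.

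**2. The plan's dropout figure.** The Protocol synopsis has 30 men entering per previous active arm, about 17% dropout and about 25 completers. 30 × 0.83 = 24.9, which reproduces. The split of these roughly 5 men around Week 36 is not given. If dropout is even over the 24 weeks, half falls in the 12 weeks before Week 36, about 8% of the arm. The maximum is 17%.

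**3. General size.** Understatement = (share unscanned) × (mean loss in unscanned men − mean loss in scanned men). Both the number of unscanned men and the gap in 12-month loss are assumptions:

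| Unscanned of 30 | Gap 1 point | 2 points | 3 points | 5 points |
|---|---|---|---|---|
| 1 | 0.03 | 0.07 | 0.10 | 0.17 |
| 2 | 0.07 | 0.13 | 0.20 | 0.33 |
| 3 | 0.10 | 0.20 | 0.30 | 0.50 |
| 5 | 0.17 | 0.33 | 0.50 | 0.83 |

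**4. Size when stopping depends on Week 24 loss.** The SD is 0.0439 g/cm² (Protocol 13.1). No baseline BMD is given; assuming 1.0 to 1.2 g/cm², the SD is 4.39% to 3.66%. Further assumptions: Week 24/Week 48 correlation 0.5 to 0.7, and logistic dropout on Week 24 loss. Simulated understatement, in percentage points:

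| Excluded | Log-odds 0.25–0.5 per SD (weak) | Log-odds 1–2 per SD (strong) |
|---|---|---|
| about 8% | about 0.03–0.12 | 0.14–0.37 |
| about 17% | not needed for the upper bound | 0.27–0.68 |

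A hand check for weak dependence is share × log-odds × correlation × SD. At the low end, 0.083 × 0.25 × 0.5 × 3.66 = 0.04, and with 2 of 30 men, 0.067 × 0.25 × 0.5 × 3.66 = 0.03. With no dependence the result is 0.

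**5. Scale.** The standard error at n = 25 is 3.66/5 = 0.73 to 4.39/5 = 0.88 points, so 0.37 is about 0.4 of a standard error (0.37/0.88 = 0.42). At SD 4.39%, n = 25 and a true loss of 6%, power is about 90%. With strong dependence it falls to about 82–87% at 8% excluded and 72–83% at 17%.

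**6. Would simply carrying Week 24 forward help?** Suppose 25 scanned men lose 2.5% and 5 unscanned men lose 6%. The test sees 2.5%; the mean for all 30 is (25 × 2.5 + 5 × 6)/30 = 3.08%. If loss is linear, half has occurred by Week 24, and carrying it forward gives (25 × 2.5 + 5 × 3)/30 = 2.58%. It recovers little.

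**7. Would a model using Week 24 help?** If stopping depends only on Week 24 loss, a regression on that loss removes the bias, but only because the simulation was built that way. If stopping depends on Week 48 loss instead, about 53–78% of the bias remains.

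**8. A window gap.** In Appendix F the Week 24 window closes on Day 196 and the Week 48 window opens on Day 308 (44 × 7). Week 36 is Day 252 (36 × 7). End-of-treatment scans from men stopping at about Weeks 36 to 44 fall in no window, so a model limited to the windowed visits would lose them.

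**The case against.** The strongest case against has four parts.

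- **Few routes link stopping to bone.** Fragility fracture is the only bone-related item among the mandatory stops in Protocol 9.3.4. There is no BMD or T-score stopping rule, no DEXA falls between Week 24 and end of treatment, and men with a T-score below −2.0 are excluded at entry, expressly to limit bone-related withdrawals (Protocol 9.2.1). This stands. A reader might infer that loss seen at Week 24 drives men off drug. The documents do not show that; general safety discretion in Protocol 9.3.5 leaves it possible and no more.
- **The larger figures need strong assumptions.** Log-odds of 1 to 2 per SD mean stopping odds 2.7 to 7.4 times higher per SD of loss, and nothing in the documents supports that. This also stands, which is why the range runs down to zero.
- **Requiring a late scan is coherent.** Protocol 7.1 calls 6 months too short to assess BMD, the sample size counts 48-week completers, and all analyses are labelled exploratory. This is a fair reason to keep the t-test. It is no reason to leave collected scans out of every test against 3%.
- **Much is already planned.** Fractures are reported as events of special interest, reasons for stopping are tabulated, and 8.7.1 would show a Week 48 mean per dose. But no test of that mean against 3% is specified, and if 8.1.1 governs the population the early stoppers disappear from the model too.

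**Conclusion.** The exclusion is certain from the text; the bias is conditional. It is zero if stopping is unrelated to bone loss. It is roughly 0.03 to 0.4 percentage points if about 8% of an arm is excluded, under weak to strong assumed dependence on Week 24 loss. It reaches about 0.7 points only if all 17% of dropouts stop before Week 36 and dependence is strong. These figures rest on an assumed baseline BMD, correlation and dropout model, none of which the documents give.

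Two stronger readings should be resisted. One is that the primary result will be biased: men who stop for haematocrit, PSA or testosterone need not lose more bone. The other is that a model using Week 24 cures the problem: that holds only if data are missing at random given the Week 24 scan, which may fail for a man who fractures later. The point supports an added analysis, not replacement of the protocol's test.

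**What to change.** Keep the protocol t-test and amend the SAP as follows.

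1. In 8.6.2, add a prespecified supporting analysis in all active-randomised Safety subjects with a baseline and any post-baseline scan (Week 24 or later). Use the repeated-measures model of 8.7.1 on percentage change. Test each dose's Week 48 least-squares mean against a 3% decrease at 1-sided 2.5%, with its 95% CI.
2. Assign end-of-treatment scans from Days 197 to 307 to an analysis visit, and say which value LOCF uses for these men.
3. Reconcile the BMD population in 8.1.1 (ITT and completer) with 8.6.2 and 8.7 (Safety).
4. Add a sensitivity analysis that assumes worse Week 48 loss in unscanned men over a stated range.
5. Tabulate unscanned men by dose, with reason for stopping and Week 24 BMD change.
6. Declare the addition in section 9.

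The cost is SAP text, one contrast per dose from a model already planned, one sensitivity analysis and one table. No new scans are needed. The downside is reliance on missing-at-random in item 1, which item 4 is there to probe.
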